· · ·	ECHO Intervention Development and Delivery, and Study
	of ECHO Intervention Effectiveness funded by:
	Department of Education
•	Family Hubs and Early Years Interventions
	[name]
	[name]
Funder(s)	[name]
	[contact]
	Manchester Local Authority
	[name]
	Manchester
Protocol V.1.1	Date: 16.05.2024 IRAS ID: 331323

	Manchester Local Care Organisation MANCHESTER CITY COUNCIL	Department for Education	Manchester University NHS Foundation Trust
		[name] [name] [name] [name]
	· · ·	Intervention Effectivene Manchester Local Author [name] Manchester	
		[name] [name] [name] [name]
	Statistician	[name] [name] [name]	
		[name] [name] [name] Greater Manchester [name] [contact] [name]	s.uk
	Key Protocol Contributors	[name] [name] The University of Manch [name] [name] [contact] [name]	
-		[name] [name] The University of Manch [name] [name] [name] [name]	
		[name] [name] [name]	nchester.ac.uk
	Protocol V.1.1	Date: 16.05.2024	IRAS ID: 331323 6

•

Manchester Local Care Organisation MANCHESTER CITY COUNCIL	Department Ma for Education	anchester University NHS Foundation Trust
 Committees	Trial Management Group (TMG) orga [name] [name] [name] Wythenshawe Greater Manchester [name] [contact] [name]	inized by:

Study Summary

	Single-cen	tre, single arm study with mixed methods:		
	Qualitative Study – in-depth qualitative interviews with			
	parents/caregivers who have received the ECHO			
Study Design	Interventio	n as part of their usual pathway of care.		
	ECHO Inte	ervention Study – prospective sample of		
		regivers receiving the ECHO Intervention to		
		ffectiveness.		
	Parents/ca	regivers with children under 24 months scoring		
	Red on We	ellComm Language Screen (indicating significant		
	language c	difficulties) and scoring High Likelihood for		
Study Participants		the Social Attention and Communication		
	Surveilland	ce (SACS-R) (Barbaro et al., 2022) tool in the		
· .	Mancheste	er Local Authority area recruited through referrals		
	to the Early	Years Communication and Language Pathway.		
	8-12 paren	ts/caregivers will be recruited for the Qualitative		
Planned Size of Sample	Study.			
-		/caregivers will be recruited for the ECHO		
Deemvitus ant Deviced	Intervention effectiveness study.			
Recruitment Period	12 months			
Follow Up Period		post-intervention follow-up		
Overall Study Duration	16 months	·		
		Assess ECHO Intervention effectiveness evidenced		
Research Question/Aim(s)	through improved communication skills of children at 12-			
	week follov			
		effectiveness of a targeted intervention (ECHO) munication skills of children under 24 months		
		cant language difficulties and social		
Study Objectives		ation difficulties. To evaluate if there is any		
	noticeable	pticeable effect of the targeted intervention on the parent-		
	child intera	ction and parent/caregiver wellbeing.		
Primary Outcome Measure	н .	Primary Endpoint		
The Communication and Symbolic	Behaviour			
Scales Developmental Profile™ (C		Score at 12-week follow-up		
Secondary Outcome Measures		Secondary Endpoints		
Qualitative interviews		Qualitative Study results collected at interview,		
		at baseline and at 12-week follow-up		
WellComm Language Screen Early		,		
Toolkit – paper version (GL Assessments,		Score at 12-week follow-up		
2015)				

Manchester Local Care Organisation MANCHESTER CITY COUNCIL	Departr for Educ		Manchester Universit	S S
The Pragmatics Profile of Everyday Communication Skills (Dewart et a	,			
The Tool to Measure Parenting Se (TOPSE) (Bloomfield et al., 2010)	lf-Efficacy			
Clinical outcome measure of paren interaction	ıt-child	Score at ea up	ch session and at 12-week follow-	

Funding and Support in Kind

Funder(s)	Financial And Non-Financial Support Given Detail financial and non-financial support given by each organisation listed	
Department of Education	Funding for ECHO Intervention Development and Delivery, and Study of ECHO Intervention Effectiveness	
Manchester Local Authority	Funding for ECHO Intervention Development, and Study of ECHO Intervention Effectiveness	

Role of Study Sponsor and Funder

Manchester University NHS Foundation Trust is acting as sponsor for this study and is assuming overall responsibility for the initiation and management of the study. The Trust will provide permission to conduct the research and monitor the progress of that research. The research team all hold substantive or honorary contracts with the Trust and therefore the sponsor has influence over all aspects of the study design, conduct, data analysis and interpretation, manuscript writing, and dissemination of results which are the responsibility of the research team.

Manchester Local Authority and Department of Education will receive results of the study and may disseminate results.

Roles and Responsibilities of Study Management Committees/Groups & Individuals

Study Steering Groups

The Trial Management Group (TMG) will meet monthly throughout the study duration to review the progress of the study, recruitment rate, general research study issues and protocol amendments. The trial management group will include the Chief Investigator, Principal Investigators, and Statistician

Key Words:

Autism; parent-child interaction; early intervention; social communication.

Abbreviations

Abbreviation	Definition
APR	Annual Progress Report
CSBS DP	The Communication and Symbolic Behaviour Scales
	Developmental Profile™
CTIMP	Clinical Trials of Investigational Medicinal Products
ECHO	Early Communication Home-Learning Offer
GCP	Good Clinical Practice
HRA	Health Research Authority
ICH GCP	International Council for Harmonisation of Technical Requirements for Pharmaceuticals for Human Use Good Clinical Practice
ID	Identification
IMD	Index of Multiple Deprivation
IQR	Inter-Quartile Range
IRAS	Integrated Research Application System
MFT	Manchester University NHS Foundation Trust
n.d.	No Date
NHS	National Health Service
PPI	Patient and Public Involvement
R&D	Research & Development
R&I	Research & Innovation
REC	Research Ethics Committee
RISOP	Research & Innovation Standard Operating Procedure
SACS-R	Social Attention and Communication Surveillance – Revised
SAE	Serious Adverse Event
SD ·	Standard Deviation
SLT	Speech and Language Therapist
SOP	Standard Operating Procedure
TMF	Trial Master File
TMG	Trial Management Group
TOPSE	The Tool to Measure Parenting Self-Efficacy

Study Flow Chart

Figure 1. Flow chart of the participant journey in the ECHO Intervention Study

T	
Constant Con	
Contraction of the local states	
	188-65
and the second	
h	
m	
m	
m	
m	
т	
m	

Referrals received from health visiting service and/or children centre services. Eligibility and recruitment at initial visit.

Inclusion criteria: Parent/caregiver of child aged under 24 months at the start of intervention; Child Scored Red on WellComm Language Screen within 3 months of the referral; Child Scored High Likelihood of autism on Social Attention and Communication Surveillance (SACS-R) tool; Residing within the Manchester Local Authority for the duration of intervention.

Exclusion criteria: The family are currently receiving intervention from another Speech and Language Therapy Service; Parent/caregiver already taking part in the trial with another child; The child or parent has a diagnosis of visual, motor, or hearing impairment; The child has a diagnosis of a developmental disorder other than autism; Current significant and ongoing safeguarding concerns.

n = 40

Measures taken at baseline visit

Primary Outcome measure: The Communication and Symbolic Behaviour Scales Developmental Profile™ (CSBS DP)

Secondary Outcome measures:

The WellComm Language Screen; The Pragmatics Profile of Everyday Communication Skills; Clinical Outcome Measure Form (child's interaction, non-verbal communication skills, and language skills); The Tool to Measure Parenting Self-Efficacy (TOPSE); A research tool developed from local clinical service recording observations of parent-child interaction

5 ECHO intervention sessions delivered weekly

(Clinical outcome measure of parent-child interaction collected each session)

DEPENDED AND	
SR (#	
	100000
•	
10000	100
	100
10000	100
	-
	-
	-
10000	-
	-
	-
	-
	-
	-
	-
	-
	-
	-
	-
	-
	-
	-
	-
	-
	-
	-
	-
	-
	-
	-
	-

Measures taken 12 weeks following intervention

Primary Outcome measure: The Communication and Symbolic Behaviour Scales Developmental Profile™ (CSBS_DP)

Secondary Outcome measures:

The WellComm Language Screen; The Pragmatics Profile of Everyday Communication Skills; Clinical Outcome Measure Form (child's interaction, non-verbal communication skills, and language skills); The Tool to Measure Parenting Self-Efficacy (TOPSE); A research tool developed from local clinical service recording observations of parent-child interaction

1. Background

1.1 Theoretical Background

Early social communication skills, including joint attention, are predictive of later language development (Charman, 2003; Mundy, P., et al. 1990). It is estimated that around 25-30% of autistic children are pre-verbal or minimally verbal in early childhood (Tager-Flusberg & Kasari 2013; Anderson et al. 2007; Rose et al. 2016). These early social and language skills are predictive of outcomes in adolescence and beyond (Gillespie-Lynch et al. 2012; Howlin et al. 2014; Magiati et al. 2014).

Research strongly suggests that interventions should commence as early as possible, even before an official autism diagnosis, particularly during toddlerhood or early childhood (French, & Kennedy 2018). Interventions are increasingly designed for infants not yet diagnosed with autism (Green et al. 2018; (Whitehouse et al. 2019; Whitehouse et al. 2021). This is based on the belief that the infant brain's neuroplasticity provides an ideal window for intervention (Kolb & Gibb 2011; McEachin et al. 1993. Additionally, there is a growing body of evidence supporting the long-term benefits of early intervention (Pickles et al. 2016). Autistic individuals, parents/caregivers, clinicians and professionals have highlighted that effective interventions for the development of language and communication is a top-three priority (Autistica, 2016).

Naturalistic developmental behavioural interventions (NDBIs) and behavioural interventions grounded in behavioural and developmental theory (Schreibman et al., 2015) offer the strongest evidence base for early autism interventions (Sandbank et al., 2020). These interventions align with normative developmental stages and emphasize the child's unique qualities, needs, and interests (Green et al., 2010; Dawson et al., 2010). They have demonstrated positive impacts on social communication skills, although their effects on direct language measures are less clear (Green et al., 2010; Kasari et al., 2015; Shire et al., 2017).

Decades of child development research (Akhtar et al., 1991; Landry et al., 2000; Page et al., 2010; Tomasello, M., & Todd, J., 1983) highlight the importance of early dyadic social interaction for later social communication and adaptation skills. The transactional model of development (Sameroff, 1975; Sameroff, 2009) underscores how a child's interactions with their parent/caregiver, central to their primary environment, shape the development of social communication, self-regulation, and other essential skills. This model does not attribute autism's cause to parent-child interactions but instead suggests that adjusting interaction styles to align with the child's attempts at engagement can support social communication development, potentially benefiting the child's long-term outcomes (Blacher et al., 2013; Doussard–Roosevelt et al 2003).

Current best clinical practices involve clinicians training parents/caregivers in intervention strategies (NICE, 2013). Evidence supports the effectiveness of parent/caregiver-mediated communication interventions on both parent-child interaction and child autism outcomes (Sandbank et al., 2020; Pickles et al. 2016). It is important to note that parent/caregiver-mediated interventions can also positively affect parents/caregivers themselves (Estes et al., 2019). These interventions provide parents/caregivers with training, empowering them with knowledge and skills to enhance communication with their child and better understand their child's behaviour. Research has shown reductions in parent/caregiver stress (Da Paz & Wallander, 2017; Ladarola et al., 2018) and improvements in family wellbeing and quality of life (Leadbitter et al., 2018). However, literature specifically addressing child wellbeing remains limited.

Manchester University NHS Foundation Trust

The ECHO targeted communication intervention, designed for children aged under 24 months with significant language difficulties related to social communication issues, is based on naturalistic developmental behavioural evidence. This study aims to assess the impact of a short-term, 5-session targeted intervention on this high-risk population and evaluate its effects on parent-child interaction, child wellbeing, and parent/caregiver wellbeing.

1.2 Local Need Assessment

In Manchester, fewer children achieve a good level of development at the end of their foundation stage compared to the national average (GOV.UK, n.d.). In a cluster of schools in a highly disadvantaged part of Manchester, 50% of the nursery sample had significant language difficulties (Ainscow, M. et al., 2012).

According to the 2019 Index of Multiple Deprivation (IMD), Manchester ranks 6 out of 326 local authorities in England, where 1 is the most deprived (Manchester City Council, n.d.). Any intervention targeting families in Manchester needs to include accommodation for families with limited resources and consider the high levels of demand on local services.

Current waiting times for NHS Speech and Language services are well above the NHS targets, especially for children presenting with social communication difficulties (Clinical data). Current waiting times for initial assessment average 32 weeks with an additional wait of 104 weeks for intervention for children with social communication difficulties. The waiting time has increased due to the pandemic and is identified as a 'key issue that will need addressing' (Manchester Parent Carer Forum, n.d.).

Manchester is also considered 'one of the most linguistically diverse cities in England and Europe' (Manchester City Council, n.d; Manchester City Council, 2024), meaning that any intervention targeting children in Manchester needs to include provision for families with multiple languages and limited English language skills. The ECHO Intervention is designed to be deliverable using interpreters and recommendations can be adapted to be delivered by caregivers in any language. Resources were designed to be accessible to families with limited English and literacy skills such as using visuals and videos.

The First 1001 Days Movement (Parent, n.d.) highlights the importance of the period from conception to age 2 on the developing brain and long-term outcomes. Manchester has an established targeted intervention for children presenting with language difficulties without social communication difficulties focused on parent/caregiver education. This intervention is the basis for the ECHO Intervention with consideration of the research literature concerning universal and targeted level strategies supporting early social communication development.

After consulting relevant research, no intervention was identified for children under 24 months presenting with social communication and language difficulties, which could be delivered in any language at the universal and targeted level, within the constraints of local resources and parent/caregiver engagement needs.

In developing the ECHO Intervention, all children in Manchester presenting with early communication difficulties can receive support within the first 1001 days.

1.3 Evidence from Local Clinical Context

Preliminary clinical data collected from delivery of the ECHO Intervention with 12 children suggests that the ECHO Intervention is effective at improving children's communication skills and parent/caregiver wellbeing. A summary of this data was shared with research funders.

After the final intervention session, parents/caregivers were asked for their perspective on their child's communication skills. All parents/caregivers reported increases in vocalisations and babbles and for some children an increase in using single words in context. All parents/caregivers reported increased use of non-verbal communication such as gestures, using objects, and using noises to communicate needs, as well as increases in eye contact and requests for shared activities. For example, children bringing bottles to ask for a drink and dancing to ask for music videos. Parents/caregivers also reported understanding their child's emotion regulation.

When asked to rate the impact of the intervention, parents/caregivers indicated they experienced improvements in their child's communication, the wellbeing of their child, and their relationship with their child. Parents/caregivers reported the most improvement in their own wellbeing.

Clinical observations noted improvements in children's social and non-verbal communication skills similar to parent/caregiver reports. Clinicians also observed fewer difficulties with transitions and sensory regulation as interventions progressed.

From these clinical data, there are indications that the ECHO Intervention produces positive impacts for children with significant communication difficulties and social communication difficulties. As well as positive impacts on children's communication development, the ECHO Intervention may have a positive impact on child and parent/caregiver wellbeing. These early indications need to be further explored to understand the potential benefits of the ECHO Intervention across a larger group of parents/caregivers.

2. Rationale

Given the evidence for development in the context of social communication differences and autism, early intervention is beneficial for this clinical population. Due to local needs, the intervention is more accessible when delivered in a short course by less specialized practitioners and individualized to family needs. For this reason, the ECHO Intervention may be an effective method of treatment for local families. This study will evaluate the effectiveness of an intervention targeting communication difficulties associated with social communication difficulties, adapted to the context of a community with high levels of deprivation and multilingualism.

3. Research Question/Aim(s)

This study aims to further develop the ECHO Intervention and assess the measurement of effectiveness, perceptions, barriers, and potential harms. It also aims to assess the effectiveness of the ECHO Intervention as evidenced through the improved communication skills of children at 12-week follow-up, and to evaluate if there is any noticeable effect of the targeted intervention on the parent-child interaction and parent/caregiver wellbeing.

3.1 Objectives

Qualitative Study Objectives:

- i. Primary Objective: Inform intervention and its measurement development, implementation, and sustainability (Reflexive Analysis (Braun & Clarke, 2006; Braun & Clarke, 2020)).
- ii. Secondary Objectives:
- o Identify perceptions of the intervention
- Identify any benefits and/or harms potentially related to the ECHO Intervention not anticipated by clinicians
- o Identify barriers to implementation and embedding of strategies.

ECHO Intervention Study Objectives:

- i. Primary Objective: To assess whether the ECHO Intervention is effective at improving child communication.
- ii. Secondary Objectives: To test whether the ECHO Intervention is effective at:
 - o Improving parent/caregiver wellbeing and efficacy
 - Increasing parent/caregiver use of parent-child interaction strategies supporting communication development
 - Increasing child's language skills
 - Increasing child's social communication skills.

3.2 Outcome Measures

Qualitative Study Outcomes:

i. In-depth semi-structured interviews with parents/caregivers who received the ECHO Intervention as part of their usual pathway of care.

ECHO Intervention Study Outcomes:

- i. Primary Outcome Measure: The Communication and Symbolic Behaviour Scales Developmental Profile™ (CSBS_DP) (Wetherby, A.; Prizant, B., 2002)
- ii. Secondary Outcome Measures, measured at baseline and 12-week follow-up (Parent-Child Interaction Pre/Post also taken at each intervention session)
- The Tool to Measure Parenting Self-Efficacy (TOPSE) (Bloomfield et al., 2010)
- Parent-Child Interaction Pre/Post Measure, a clinical tool used in current clinical practice to measure parent-child interaction strategy use
- WellComm Language Screen Toolkit Early Years Paper version (GL Assessments, 2015)
- The Pragmatics Profile of Everyday Communication Skills (Dewart, H., & Summers, S., 1995) to measure changes in child's communication skills

3.2.1 Rationale for Outcome Measures

Outcome measures were selected based upon whether they were suitable for the clinical population. Specific consideration was given to their suitability:

- for the targeted age range,
- for families with languages other than English, and
- for families from similar cultures and ethnicities as the Manchester population.

Consideration was given for the time that outcome measures may take to complete, as children and parents of young children may find it difficult to attend for long periods of time.

Outcome measures were also selected to allow for the views of parents as well as clinical observation, since some children may behave differently during clinical sessions and parents may interpret children's communication differently based on their knowledge of the child and their family's cultural norms.

The Communication and Symbolic Behaviour Scales Developmental Profile[™] (CSBS DP) (Wetherby, A.; Prizant, B., 2002) was selected as the primary outcome measure as it is a validated tool standardized for children aged 6-24 months and it was likely to be sensitive to detect small to changes across different early communication skills.

1. Study Design and Methods of Data Collection

4.1 Study Design

A single-centre, one arm design using mixed-methodology including parent/caregiver reports, clinical observations and in-depth semi-structured interviews. Parents/caregivers taking part in the effectiveness study will access the ECHO Intervention as part of their usual pathway of care and will be able to access all other services and interventions on offer in their locality for the duration of their participation in the study. All participants recruited to the study will be offered the ECHO Intervention. At present, the ECHO Intervention is the only intervention available in the standard pathway of care, and thus a no-treatment contro is not deemed ethical given the hypothesised benefits on the parent/caregiver and child outcomes.

4.2 Methods of Data Collection

Qualitative Study

Interviews will be completed using the ECHO Interview Schedule. Interviews will be conducted over Zoom and will be recorded.

When scheduling interviews, participants will be informed that children cannot be present for the duration of the recorded interview. If a child is present during the interview, recordings will be paused until the child is no longer present. Participants will be asked to avoid saying identifiable information during the interview.

If families cannot access the Zoom interview because of IT access, a member of the child's direct care team will attend face-to-face to support the family to access the interview. This could include support with how to access zoom using devices in the family home. It could

Date: 16.05.2024

IRAS ID: 331323

Manchester Local Care Organisation MANCHESTER CITY COUNCIL

Department

Manchester University NHS Foundation Trust

also include providing an MFT Laptop to access Zoom. If an MFT laptop is provided, no log in information will be shared, an MFT staff member will be present to ensure the laptop is used correctly and only zoom is accessed, and the laptop will not be connected to any systems that can access confidential information. If internet connection is a concern, families can be invited to a private room at a children's centre to access the Zoom interview.

Only audio recording will be collected from Zoom. Audio recordings will be saved to MFT servers which are password protected to NHS standards. Audio recordings will be labelled using the following format: ECHO Interview Date of interview (DD.MM.YY) Participant number (for example ECHO Interview 05.09.23 P01). Only study staff in the clinical team and authorised personnel will have access to the study folder.

Zoom will be used to create transcripts of audio recordings. Transcripts will be saved to MFT servers in the same folder as audio recordings. Transcripts will be labelled using the same format as audio recordings.

The study staff will ensure that the participants' anonymity is maintained. The study will comply with the Data Protection Act which requires data to be pseudonymised as soon as it is practical to do so with the participant identification number. Audio files and transcripts will be reviewed as soon as possible to correct transcription errors and remove identifiable information in the transcript. Reviews will be completed by the interviewer and checked by another member of the research team. Once the review is complete and the transcript is anonymised, audio files will be stored as source data in secured folders with access restricted to study research members on MFT servers. Only pseudonymised transcript data will be shared for analysis.

ECHO Intervention Study

Data collection will be carried out by clinicians working on the ECHO Intervention study within the Early Years Communication and Language Team in accordance with Good Clinical Practice procedures. Baseline and endpoint measures will be collected by Speech and Language Therapists within the research team. Intervention data will be collected by the Language Development Workers delivering the ECHO Intervention. All staff will attend Good Clinical Practice training and be trained in the study protocol by the Chief Investigator.

All study visits will take place at the parent/caregiver's home, or another suitable location if preferred. A Language Development Worker may be present to support any children while parents/caregivers are answering questionnaires. Paper copies of outcome measures will be stored in a locked cabinet on MFT property and data will be entered by the clinician who collected the data into the research Excel database stored on MFT servers.

Researchers will be present during the completion of research assessments and will support parents/caregivers in understanding and completing assessments. Where appropriate, interpreters will be present to support parents/caregivers to understand and complete assessments.

At each intervention visit, the Language Development Worker providing the intervention will complete observations of parent-child interaction using the Parent-Child Interaction Pre/Post Measure tool. As with baseline and endpoint measures, paper copies of outcome measures will be stored in a locked cabinet on MFT property and data will be entered in the research Excel database stored on MFT servers by the clinician who collected the data.

Manchester Local Care Organisation MANCHESTER CITY COUNCIL

Department for Education

Manchester University NHS Foundation Trust

At the review appointment, a Speech and Language Therapist will collect the endpoint outcome measures through observations and parent/caregiver questionnaires. A Language Development Worker may be present to support any children while parents/caregivers are answering questionnaires. Paper copies of outcome measures will be stored in a locked cabinet on MFT property and data will be entered in the research Excel database stored on MFT servers by the clinician who collected the data.

All study data will be pseudonymised with a study identification (ID). A paper central master file of personal data will be held securely in the Early Years Communication and Language Team office only accessible to trained members of the Early Years Communication and Language Team to be used for operational purposes. This central master file will contain the key linking anonymised participant IDs to personal details. Study data will be entered into the research database by the research staff member who collected the data, with data checking procedures detailed in the database guidance documents adhered to by the delegated research staff member. Appropriate quality control will be carried out during the study and before the database lock at the end of the study. Quantitative data analysis will be undertaken by the study Statistician and Chief Investigator. The Principal Investigators will also have access to the data and will undertake analysis as appropriate and necessary. The Principal Investigators will be responsible for qualitative analysis of the data. The Principal Investigators and study Statistician will store and process pseudonymised data for the purpose of analyses in their personal area of University of Manchester systems in folders only accessible to themselves and stored in compliance with the Data Protection Impact Assessment (DPIA) form approved by MFT Research Department.

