5.3.2 Sampling Technique

Participants will be selected using a convenience sampling technique from all eligible patients accessing the Early Years Communication and Language Pathway. This sampling technique is used as there is only a small population of participants who can be identified using available resources for this study. Convenience sampling is a more cost-effective method of sampling for a study of this scope (Jager et al., 2017). A convenience sampling technique will limit generalizability (Jager et al., 2017) and further research will be necessary if the study demonstrates effectiveness in this limited sample.

Manchester University NHS Foundation Trust

This study is not blinded as there is no comparison group. The intervention will be delivered by different staff to those collecting baseline and endpoint measures to reduce potential bias.

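### The worker who delivered a family's ECHO sessions is not excluded from the review visit, so the separation of deliverers from outcome collection is incomplete for parent-reported outcomes

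*Protocol*

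**What the plan says.** All references are to the protocol.

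- **Blinding and safeguard (5.3.2).** "This study is not blinded as there is no comparison group". The next sentence gives the protection relied on instead: "The intervention will be delivered by different staff to those collecting baseline and endpoint measures to reduce potential bias".
- **Who delivers (4.2).** "Intervention data will be collected by the Language Development Workers delivering the ECHO Intervention". Section 5.5 likewise places the sessions with a Language Development Worker.
- **Who collects outcomes (4.2).** "Baseline and endpoint measures will be collected by Speech and Language Therapists within the research team". For the endpoint: "At the review appointment, a Speech and Language Therapist will collect the endpoint outcome measures through observations and parent/caregiver questionnaires".
- **Who else may be in the room (4.2).** "A Language Development Worker may be present to support any children while parents/caregivers are answering questionnaires". This sentence appears twice, once in the paragraph on study visits in general and once in the paragraph on the review appointment.
- **Help with the forms (4.2).** "Researchers will be present during the completion of research assessments and will support parents/caregivers in understanding and completing assessments". The term for these staff is not defined further.

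**The concern.** Separating deliverers from assessors protects a therapist-scored observation because the scorer has no stake in that family's sessions. For a questionnaire, the parent's answer is itself the datum. The separation then protects only if the parent also answers away from the person who delivered the programme. A worker who scores nothing can still influence the answers by being present, since a parent may rate their own confidence or their child's progress more favourably in front of someone who has spent five sessions helping them.

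The analysis is an uncontrolled before-after comparison. A shift in answers that occurs at review but not at baseline goes straight into the estimated change, and no second arm shares it. It arises from how the visit is run, so it cannot be removed in analysis afterwards.

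**Working it through.** The protocol gives no figure on this point, so the check is a comparison of its sections.

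1. **Is the worker at review from the delivering staff group?** Yes. Sections 4.2 and 5.5 give delivery to Language Development Workers, and 4.2 names the same role for child support at review.

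2. **Is the family's own worker excluded?** No. Sections 4.2, 4.3, 5.3.2 and 5.5 contain no such rule. The audit visits in 7.6 check adherence to the manual and protocol, and with no rule on attendance there is nothing on this for them to check. No section asks for attendance to be recorded.

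3. **Which outcomes are exposed?**
   - TOPSE: a parenting self-efficacy score, compared between baseline and endpoint with a paired test (6.1).
   - Pragmatics Profile: parents' own descriptions of the child's communication, analysed descriptively (6.1).
   - CSBS DP (primary) and WellComm: exposed only as far as they draw on parent report. Section 4.2 says endpoints come from both observation and questionnaires, but does not divide the individual measures between the two.
   - Parent-child interaction measure: an observation tool, collected at baseline and review by a therapist. The mechanism above does not apply to it directly.

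4. **Is the exposure the same at both timepoints?** Presence is allowed at both, because the sentence also covers study visits in general. The relationship differs. The schedule in 4.3 puts baseline ahead of session 1 (5.5 allows both on one day), so a worker present at baseline has not yet treated the family. Review comes 12 weeks after session 5, with 4 weeks' leeway either way, that is 12 − 4 = 8 to 12 + 4 = 16 weeks. By then a returning worker has delivered the programme.

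5. **How would it enter the result?** Let *p* be the share of reviews attended by the family's own deliverer, and *δ* the mean shift in a parent-reported score caused by that person's presence as deliverer. Then

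   expected observed change = change without that influence + *p* × *δ*.

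   Any effect of having a worker in the room at all cancels to the extent that a worker attends both visits. The term *p* × *δ* has no baseline counterpart. The protocol gives neither *p* nor *δ*, so the product cannot be calculated.

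6. **Does it affect a stated figure?** No. The sample-size inputs in 5.3.1 (40 families, 10% dropout, effect size 0.48, alpha 0.05, 80% power) do not depend on who attends.

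**The case against.** The case on the other side is substantial.

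- **The wording is indefinite.** Section 4.2 refers to a worker of that grade. When it means the deliverer it says so: "At each intervention visit, the Language Development Worker providing the intervention will complete observations of parent-child interaction". A reader might infer that the deliverer is expected to attend the review. The text does not support that; it leaves the possibility open. This stands.
- **The safeguard is kept as written.** A reader might infer that 4.2 contradicts 5.3.2 or cancels its protection. It does neither. The safeguard concerns who collects the measures, and therapists collect them all. The worker's only stated task at review is child support. This stands.
- **Other courtesy effects exist anyway.** The therapist belongs to the research team, parents know they received ECHO, and researchers help with the forms. The added effect of one more person may be small. Where possible, parents also receive outcome forms in advance (7.5), which may dilute it. This bears on size, but it does not close the gap.
- **The study is modest in its claims.** Section 6.1 calls the analysis hypothesis generating and concedes that maturation cannot be controlled. That lowers the stakes. Unlike maturation, however, this influence can largely be avoided by rostering.
- **The ECHO Manual might cover attendance.** It is cited but not shown. Even so, a rule that completes a safeguard stated in the protocol belongs beside it.

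It is also tempting to assume a shift in standard-deviation units and turn it into a false-positive rate for the 36 expected pairs (40 × 0.9). That would not measure the problem. The shift would be invented, the share of affected reviews is unknown, and the effect size of 0.48 is not given for TOPSE, the clearest exposed outcome with a test.

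**Conclusion.** The point holds as a gap in the safeguard. The separation in 5.3.2 covers who collects outcomes but not who is present when parents answer, and 4.2 allows that person to be the family's own deliverer. It is therefore incomplete for TOPSE, for the Pragmatics Profile and for whatever part of the other measures rests on parent report. It does not show that therapist-observed scores lose their protection, nor that the primary outcome is biased.

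If there is an effect, it would most plausibly favour ECHO, because only at review can the parent be facing someone who has treated the family. This rests on two assumptions that the protocol does not test: that some families' own workers attend the review, and that their presence makes answers more favourable. The size is unknown. No sample-size, alpha or power figure changes. This is an inexpensive improvement to trial conduct, worth making because analysis could not repair the bias later.

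**What to change.** In section 4.2, beside the sentence that allows a worker to attend the review, add wording such as:

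> Where rostering allows, a Language Development Worker supporting the child at the review visit will not be one who delivered ECHO sessions to that family. The case report form will record which staff attended the review and whether any of them delivered ECHO to the family.

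The attendance record lets reviews with the deliverer present be counted and identified when parent-reported change is described. It would not correct for the influence, since attendance is not assigned at random.

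**Cost:** one protocol amendment, one field on the case report form and some loss of scheduling flexibility. The child may also lose a familiar worker at that visit. The protocol does not state how many Language Development Workers there are, so the rule should stay conditional on rostering and should not require extra staff.
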